2 PROTOCOL SYNOPSIS

Title A Phase 3 Study Evaluating the Pharmacokinetics, Safety, and Tolerability of VX-659/TEZ/IVA Triple Combination Therapy in Cystic Fibrosis Subjects 6 Through 11 Years of Age

Brief Title Evaluation of VX-659/TEZ/IVA in Cystic Fibrosis Subjects 6 Through 11 Years

Clinical Phase and Clinical Study Type

Phase 3, pharmacokinetic (PK), safety, and tolerability

Objectives

Part A

Primary Objective

To evaluate the PK of VX-659, tezacaftor (TEZ), and ivacaftor (IVA) when dosed in triple combination (TC)

Secondary Objectives

- To evaluate the PK of TEZ and IVA metabolites
- To evaluate the safety and tolerability of VX-659/TEZ/IVA

Endpoints Part A

Primary Endpoint

PK parameters of VX-659, TEZ, and IVA, including C_{max}, C_{trough}, and AUC_{0-T}

Secondary Endpoints

- PK parameters of TEZ and IVA metabolites, including C_{max}, C_{trough}, and AUC_{0-τ}
- Safety and tolerability as determined by adverse events (AEs), clinical laboratory values, standard 12-lead ECGs, vital signs, and pulse oximetry

Number of Part A Subjects

Approximately 12 subjects are planned for enrollment.

Study **Population**

Male and female cystic fibrosis (CF) subjects 6 through 11 years of age who are homozygous for F508del (F/F genotype) or heterozygous for F508del and a minimal function mutation that is not responsive to TEZ, IVA, or TEZ/IVA (F/MF genotypes).

Investigational

Part A Drug

Active substance: VX-659/TEZ/IVA

Activity: CFTR correctors (VX-659 and TEZ) and CFTR potentiator (IVA) (increased chloride ion secretion)

Strength and route of administration: 120-mg VX-659/50-mg TEZ/75-mg IVA fixed-dose combination (FDC) tablet for oral administration AND 75-mg IVA tablet for oral administration

Dose administered:

VX-659 120 mg qd/TEZ 50 mg qd/IVA 75 mg q12h; $1 \times VX$ -659/TEZ/IVA FDC tablet in the morning and $1 \times IVA$ tablet in the evening

Study Duration

Part A

Excluding the Screening Period, subjects will participate in the study for up to 6 weeks (± 7 days)

Study Design

This is a Phase 3, 2-part (Parts A), multicenter study evaluating the PK, safety, and tolerability of VX-659/TEZ/IVA TC therapy in CF (F/F and F/MF genotypes) subjects 6 through 11 years of age (inclusive).

[figure not shown]
Part A

A schematic of the study design for Part A is provided below. Approximately 12 subjects (F/F or F/MF genotypes) are planned for enrollment. During the Treatment Period, subjects will be administered VX-659/TEZ/IVA for approximately 15 days. A review of safety, tolerability, and available PK data will be completed by an internal Vertex team after Part A

Additional subjects may be enrolled as needed in Part A,

based on emerging PK data,

[figure not shown]
Part A Study Design

IVA: ivacaftor; n: number of subjects; TEZ: tezacaftor

VX-659/TEZ/IVA will be administered from Day 1 through Day 15. On Day 15, only the morning dose will be administered.

Parts A Doses			
Subjects Weight	VX-659 Dose	TEZ Dose	IVA Dose
Part A			
All weights	$120 \mathrm{mg} \mathrm{qd}$	50 mg qd	75 mg q12h

IVA: ivacaftor; qd: daily; q12h: every 12 hours; TEZ: tezacaftor

[figure not shown]
Assessments Parts A

PK Assessments:

- PK parameters for VX-659, TEZ, and IVA
- PK parameters for TEZ and IVA metabolites

Safety Assessments:

AEs, clinical laboratory assessments (serum chemistry, hematology, coagulation studies, and urinalysis), standard 12-lead ECGs, vital signs, pulse oximetry, ophthalmologic examinations, and physical examinations (PEs)

Statistical Analyses

Data from Parts A will be analyzed separately.

Part A

Approximately 12 subjects will be enrolled in Part A. Sample size calculations were determined based on VX-659 PK using noncompartmental analysis-based parameters, such as clearance and volume of distribution. Based on the variability observed in adults, data from 12 subjects will allow 80% power to target a 95% CI within 60% and 140% of the geometric mean estimate of clearance for VX-659.

3 SCHEDULE OF ASSESSMENTS

The schedules of assessments are shown in Table 3-1 (Part A Screening Period), Table 3-2 (Part A Treatment Period and Safety Follow-up Visit),

Table 3-1 VX18-659-106, Part A Screening Period

Assessment	Screening Visit (Day -28 to Day -1)	Comments
Informed Consent (and Assent)	X	
Demographics	X	Section 11.1 for details
Medical History	X	Section 11.1 for details
Ophthalmologic Examination	X	Conducted by an ophthalmologist or optometrist (Section 11.5.5)
Full Physical Examination	X	Section 11.5.3 for details
Weight, Height, and BMI	X	Weight and height will be measured with shoes off (Section 11.4.4)
Vital Signs	X	Collected after the subject has been at rest for at least 5 minutes (Section 11.5.3)
Pulse Oximetry	X	Collected after the subject has been at rest for at least 5 minutes (Section 11.5.3)
Standard 12-lead ECG	X	Performed after the subject has been at rest for at least 5 minutes (Section 11.5.4)
Spirometry	X	Performed pre- or post-bronchodilator (Section 11.4.1). Screening spirometry evaluation may be repeated, as specified in (Section 9.1.1.1).
CF Genotype (all subjects)	X	If the CFTR genotype result is not received before the first dose of study drug, a previous CFTR genotype laboratory report may be used to establish eligibility (Section 8.1). Subjects who have been enrolled whose screening genotype does not confirm study eligibility must be discontinued from the study (Section 9.9).
Serum Pregnancy Test (females of childbearing potential)	х	Females of childbearing potential is defined as females 10 years of age and older (Section 11.5.6)
Serum Chemistry	X	Section 11.5.2 for details
Hematology	X	Section 11.5.2 for details
Coagulation Studies	X	Section 11.5.2 for details
Urinalysis	X	Section 11.5.2 for details
Drug Test (urine only)	X	Section 11.5.2 for details
Alcohol Test (urine only)	X	Section 11.5.2 for details
Inclusion/Exclusion Criteria Review	X	Section 8 for details
Medication Review	X	
AEs and SAEs	X	Continuous, From Signing of ICF (and Assent Form)

Protocol VX18-659-106, Version 1.0

Table 3-2 VX18-659-106, Part A Treatment Period and Safety Follow-up Visit

Assessment ^a	Day 1	Day 2	Day 4 (± 1 Day)	Day 8 (± 1 Day)	Day 15 (± 1 Day)	ETT Visit	Safety Follow-up Visit 28 (± 7) Days After the Last Dose of Study Drug	Comments
Clinic Visit	X	X		X	X	X	X	
Telephone Contact			X					
Inclusion and Exclusion Criteria Review	X							Section 8 for details
Safety Assessments								
Full Physical Examination	х				х	X	X	Section 11.5.3 for details. Symptom-directed physical examinations will occur at any time during the study if deemed necessary by the investigator
Vital Signs	Х	Х		X	Х	X	X	Collected after the subject has been at rest for at least 5 minutes (Section 11.5.3)
Pulse Oximetry	X	X		X	х	X	x	Collected after the subject has been at rest for at least 5 minutes (Section 11.5.3)
Standard 12-lead ECG	X (triplicate)	X			x	X	X	Performed after the subject has been at re- for at least 5 minutes and before the AM dose (Section 11.5.4)
Pregnancy Test (females of childbearing potential)	X (urine)				X (urine)	X (urine)	X (urine)	Females of childbearing potential is defined as females 10 years of age and older (Section 11.5.6)
Serum Chemistry	X			X	X	X	X	Section 11.5.2 for details.
Hematology	X			X	X	X	X	Section 11.5.2 for details.
Coagulation Studies	X				X			Section 11.5.2 for details.
Drug Test (urine only)	X							Section 11.5.2 for details.
Alcohol Test (urine only)	X							Section 11.5.2 for details.
Observation 4 hours After the Morning Dose	X							
Concomitant Medications	Con	tinuous, Fro	om Signing of ICF	(and Assent For	rm) Through (Completion of S	tudy Participation	

All assessments will be performed before study drug dosing (within 60 minutes) unless noted otherwise.

Vertex Pharmaceuticals Incorporated

Protocol VX18-659-106, Version 1.0

Table 3-2 VX18-659-106, Part A Treatment Period and Safety Follow-up Visit

				Day 8	Day 15		Safety Follow-up Visit 28 (± 7) Days After the	
Assessment ^a	Day 1	Day 2	Day 4 (± 1 Day)	•	(± 1 Day)	ETT Visit	Last Dose of Study Drug	Comments
Concomitant Treatments and Procedures					rm) Through (tudy Participation	
AEs and SAEs	Con	tinuous, Fro	m Signing of ICF	(and Assent For	m) Through (Completion of S	tudy Participation	Section 13.1
PK Assessments								
PK Sampling	х			х	X			Day 1: before the AM dose, and at 1, 2, 4, and 6 hours after the AM dose Day 8: before the AM dose Day 15: before the AM dose, and at 1, 2, 4, and 6 hours after the AM dose If study drug is not administered on the day of the visit (i.e., study drug interruption or permanent discontinuation of study drug), only 1 PK blood sample will be collected. See Table 11-1 for details.
Study Drug Administration								
Meal(s) or Snack(s) at Site	х	х		х	х			Fat-containing food such as a standard "CF" meal or snack will be provided at the site to subjects after all predose assessments have occurred. Section 9.6.1 for details.
VX-659/TEZ/IVA			Day 1 Through I rning dose only o	•				Administered within approximately 30 minutes of consuming fat-containing food (e.g., standard "CF" meal or snack) (Section 9.6.1). On scheduled visits, the AM dose of study drug will be administered at the site after predose assessments have been completed (food to be provided by site on these days).

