7 STUDY ENDPOINTS

7.1 Primary Endpoints

Part A

PK parameters of VX-659, TEZ, and IVA, including $C_{\text{max}},\,C_{\text{trough}},$ and $AUC_{\text{0-}\tau}$

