9.6 Administration

9.6.1 Dosing

Part A

On Day 1 through Day 15, VX-659/TEZ/IVA will be orally administered with water. On Day 15, only the morning dose of VX-659/TEZ/IVA will be administered.

Study drug should be administered within approximately 30 minutes of the start of a fat-containing snack or meal, such as a standard "CF" meal or snack according to the following guidelines:

- 1. Morning dose of study drug will be administered at the site on Days 1, 2, 8, and 15.
- 2. Study drug will be administered after all predose assessments have been performed.
- 3. All doses of study drug (morning and evening, as applicable) should be administered at approximately every 12 hours (± 1 hour) on each dosing occasion (e.g., if the morning doses of study drug are administered at 08:00 hour on Day 1, all subsequent morning doses should be administered between 07:00 hour and 09:00 hour).
- 4. Study drug tablets will be administered within 5 minutes of each other.
- 5. Study drug will be administered with approximately 240 mL (approximately 1 cup, 8 ounces, or half a pint) of water.
- 6. At the Day 1 Visit, all subjects will be observed for 4 hours after the morning dose of the study drug.
- 7. The date, amount taken, and time of study drug administration including whether food was taken with each dose, will be recorded for 2 days before PK sample collection and on the days of PK sample collection.

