12.1 Sample Size and Power

Part A

Approximately 12 subjects will be enrolled in Part A. Sample size calculations were determined based on VX-659 PK, using noncompartmental analysis (NCA)-based parameters, such as clearance and volume of distribution. Based on the variability observed in adults, data from 12 subjects will allow 80% power to target a 95% CI within 60% and 140% of the geometric mean estimate of clearance for VX-659.

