12.4 Clinical Pharmacology Analysis

12.4.1 Pharmacokinetic Analysis

Parts A

The PK analysis of VX-659, TEZ, MI-TEZ, IVA, and M1-IVA may be performed using nonlinear mixed effects modeling and/or standard noncompartmental analysis, as data allow. Metabolites may be included in the analyses as supported by data. Descriptive statistics will be used to summarize PK parameter values for all analytes.

A detailed description of the planned PK analysis will be presented in the CPAP.

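### Does PK sampling that stops 6 hours after a once-daily dose put the primary AUC0-τ and the clearance behind the sample size out of reach?

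*Protocol*

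**What the plan says.** The synopsis gives the regimen as "VX-659 120 mg qd/TEZ 50 mg qd/IVA 75 mg q12h", so τ is 24 h for VX-659 and TEZ and 12 h for IVA. Section 7.1 makes "PK parameters of VX-659, TEZ, and IVA, including" Cmax, Ctrough and AUC0-τ the primary endpoint. No study day is attached to AUC0-τ, and volume of distribution is not listed there or in Section 7.2.

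Table 3-2 sets the sampling: "Day 1: before the AM dose, and at 1, 2, 4, and 6 hours after the AM dose Day 8: before the AM dose", then "Day 15: before the AM dose, and at 1, 2, 4, and 6 hours after the AM dose". There is no PK sample on Day 2, although Section 9.6.1 says "Morning dose of study drug will be administered at the site on Days 1, 2, 8, and 15".

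Section 12.1 states: "Sample size calculations were determined based on VX-659 PK, using noncompartmental analysis (NCA)-based parameters, such as clearance and volume of distribution". It then claims, from adult variability, 80% power with 12 subjects for a 95% CI lying within 60% and 140% of the geometric mean clearance of VX-659.

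Section 12.4.1 says the PK analysis "may be performed using nonlinear mixed effects modeling and/or standard noncompartmental analysis, as data allow", and leaves the detail to the clinical pharmacology analysis plan (CPAP), which is not at hand. Section 12.4.2 assumes a final population PK model with individual Bayesian estimates.

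**The concern.** AUC over 24 hours appears to be wanted from a profile that ends at 6 hours. For VX-659 and TEZ, 18/24 = 75% of the interval is unsampled, and for IVA 6/12 = 50%. NCA volume needs a terminal slope, and at most the 4-h and 6-h points are likely to lie beyond the peak. On Day 1 no 24-h value is drawn, although the child is in the clinic on Day 2 just before the next morning dose. Section 12.1 nevertheless uses NCA language for the sample size, and Section 12.4.1 leaves NCA and modelling side by side.

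If AUC0-τ and clearance could not be estimated, Part A would fail in its purpose of confirming the doses, and the stated precision would belong to a method the schedule cannot support.

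**Working it through.** **1. The plan's own figure.** Take power as the probability that the half-width of the 95% CI on the log scale is no more than ln 1.4 = 0.336, the tighter of the two limits:

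power = P[χ²(11) ≤ 11·m²/σ²], with m = ln 1.4·√12 / t(0.975, 11) = 0.336 × 3.464 / 2.201 = 0.530 and σ² = ln(1 + CV²).

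The protocol does not state the CV. Solving for 80% gives CV ≈ 48% (σ = 0.459). At other values:

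| CV | Power, N = 12 |
|---|---|
| 40% | 96% |
| 45% | 88% |
| 50% | 76% |
| 60% | 47% |

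The claim is plausible and cannot be checked further. It is made for clearance only.

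**2. Is Day 15 at steady state?** Fourteen daily doses precede it. With a half-life as long as 24 h, the fraction of steady state reached is 1 − 2⁻¹⁴ = 99.99%. The predose concentration on Day 15 can therefore stand for the concentration at the end of that interval, and the Day 8 and Day 15 predose values allow a check.

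**3. NCA on Day 15.** Half-life and absorption rate are assumptions: one compartment, half-lives 6, 12 and 24 h, ka 0.2, 0.4, 0.8 and 1.2 per h (12 scenarios). With k = ln 2/half-life and unit dose/volume,

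C(t) = ka/(ka − k) · [e^(−kt)/(1 − e^(−kτ)) − e^(−ka·t)/(1 − e^(−ka·τ))], and true AUC0-τ = 1/k.

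One case in full (half-life 12 h, ka 0.8 per h, τ = 24 h):

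- Concentrations at 0, 1, 2, 4 and 6 h: 0.359, 0.872, 1.063, 1.097, 1.007. The 24-h value is set to 0.359.
- Linear-up/log-down pieces: 0.616 + 0.967 + 2.159 + 2.103 + 11.314 = 17.16.
- Plain linear, last piece (1.007 + 0.359) × 9 = 12.30: total 18.15.
- True value 1/0.05776 = 17.31, so the ratios are 99% and 105%.

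Across the 12 scenarios:

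| | τ = 24 h | τ = 12 h |
|---|---|---|
| Share of AUC after 6 h | 52% to 75% | 37% to 49% |
| Linear-up/log-down ÷ true | 91% to 100% | 98% to 100% |
| Plain linear ÷ true | 97% to 116% | 99% to 100% |

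So AUC0-τ, and clearance as dose/AUC0-τ, can be obtained. A half-life as short as 4 h takes the plain linear rule to 128% at τ = 24 h, while log-down stays at 92% or above for ka of 0.3 to 1.2 per h.

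**4. Day 1 and NCA volume.** Here the concern is correct. For half-lives of 6 to 24 h and ka of 0.3 to 1.2 per h, AUC0-6 is only 20% to 48% of the Day 1 AUC0-24. In 5 of the 12 scenarios above the Day 1 curve is still rising from 4 to 6 h (all with ka of 0.2 or 0.4 per h). Elsewhere the apparent half-life is too long, for example 18.6 h for a true 12 h at ka 0.8. Neither quantity is a named endpoint.

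**5. What a Day 2 sample would add to a population estimate.** To first order on the log scale, SE(log CL) = √{(ω² + s²·[(JᵀJ)⁻¹]₁₁)/12}, where J holds the sensitivities of log concentration to log CL, log V and log ka at the scheduled times. Assume residual s = 0.20 and ω = 0.459 from step 1. The floor, with every child's clearance known exactly, is 0.459/√12 = 0.1325. The planned schedule gives 0.134 to 0.137 over the same 12 scenarios. Adding a 24-h sample lowers this by 0.1% to 0.9%. With ω = 0.30 the largest reduction is 2.1%.

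**The case for a change.** The strongest case for a change is that the predose substitution is written nowhere in the visible protocol. It relies on a Day 14 dose taken at home with a ±1 h window, and Section 9.6.2.1 allows a late morning dose. Section 12.1 names volume, which this schedule does not support by NCA. With about 12 children, the choice of method should not stay open until shortly before data lock, and naming population PK in Section 12.4.1 would cost a sentence.

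Part of this stands. NCA volume and a Day 1 AUC0-24 are not reliably estimable, and the 6-to-24-hour stretch on Day 15 is interpolated, not observed.

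The rest carries less weight. Section 9.6.1 has dose times recorded for the two days before and on each PK day, so a late Day 14 dose would be known and a model can use its actual time. Volume appears in Section 12.1 only as an example, and the sentence can be read as describing where the adult variability came from. Naming population PK would pick one of two methods already permitted, a choice the protocol assigns to the CPAP. Some sentences around the PK sections are also cut in the public text, so method detail may have been removed.

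The Day 2 draw would make a Day 1 AUC0-24 estimable for the once-daily drugs, but it adds nothing between 6 and 24 h on Day 15. For IVA it follows an evening dose and so does not close the first interval. Table 3-2 has no other blood draw on Day 2, so it would be an extra venepuncture in children aged 6 to 11.

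**Conclusion.** No change to the plan follows. The schedule is sparse, but AUC0-τ and clearance remain within reach. NCA on Day 15 is off by about −9% to 0% (log-down) or −3% to +16% (linear) for the once-daily drugs, and by 2% or less for IVA. That is modest beside the 60% to 140% limits in Section 12.1. Population modelling, which is permitted, loses almost nothing on clearance to the missing late samples. Stopping at 6 h in young children is a fair trade of sampling burden against information, and the choice of estimator is a gap that the CPAP can sensibly fill. The mention of NCA volume is loose wording with no endpoint or stated precision resting on it.

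The sizes rest on assumed one-compartment kinetics, half-lives of 6 to 24 h, absorption rates of 0.2 to 1.2 per h, steady state on Day 15 and, for the modelling check, 20% residual error. The protocol gives none of the kinetic values. A much shorter half-life would argue for log-down integration or the model over the plain linear rule, still within what Section 12.4.1 allows. No figure in the protocol is shown to be wrong.

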Table 10-1	Study Drug: Strength/Dosing Form/Route	
Table 11-1	Acceptable Pharmacokinetic Sampling Windows	
Table 11-2	Safety Laboratory Test Panels	
Table 11-3	Acceptable Methods of Contraception	52
T 11 12 1		
	Grading of AE Severity	
Table 13-2	Classifications for AE Causality	
Table 13-3	Classifications for Study Drug Action Taken With Regard to an AE	
Table 13-4	Classifications for Outcome of an AE	64
List of Fig	ures	
Figure 9-1	Part A Study Design.	27
rigure	Turri Study Design.	

List of Abbreviations

LIST OF ADDIEVIATIONS		
Abbreviation	Definition	
AE	adverse event	
ALP	alkaline phosphatase	
ALT	alanine transaminase	
AST	aspartate transaminase	
AUC	area under the concentration versus time curve	
BMI	body mass index	
CF	cystic fibrosis	
CFTR	CF transmembrane conductance regulator gene	
CFTR	CF transmembrane conductance regulator protein	
CI	confidence interval	
CI ⁻	chloride ion	
C_{max}	maximum observed concentration	
CPAP	clinical pharmacology analysis plan	
CRF	case report form	
CSR	clinical study report	
CTCAE	Common Terminology Criteria for Adverse Events	
C _{trough}	predose concentration	
CYP	cytochrome P450	
ECG	electrocardiogram	
EDC	electronic data capture	
EENT	eyes, ears, nose, and throat	
ETT	Early Termination of Treatment	
F508del	CFTR gene mutation with an in-frame deletion of a phenylalanine codon corresponding to position 508 of the wild-type protein	
F/F	homozygous for F508del	
F/MF	heterozygous for F508del and a minimal CFTR function mutation	
FAS	Full Analysis Set	
FDA	Food and Drug Administration	
FDC	fixed-dose combination	
FEV ₁	forced expiratory volume in 1 second	
FSH	follicle-stimulating hormone	
GCP	Good Clinical Practice	
GGT	gamma-glutamyl transferase	
GLI	Global Lung Function Initiative	
GPS	Global Patient Safety	
HBE	human bronchial epithelial (cells)	
HIPAA	Health Insurance Portability and Accountability Act	

	· · ·
Abbreviation	Definition
HR	heart rate
ICF	informed consent form
ICH	International Council for Harmonization
IEC	independent ethics committee
IND	investigational new drug
IRB	institutional review board
IVA	ivacaftor
IWRS	interactive web response system
M1-TEZ	metabolite of TEZ
max	maximum value
MedDRA	Medical Dictionary for Regulatory Activities
MF	minimal CFTR function mutation
min	minimum value
MMRM	mixed-effects model for repeated measures
N	number of subjects
NCA	noncompartmental analysis
OATP1B1	organic anion transporting polypeptide 1B1
P	probability
PD	pharmacodynamic, pharmacodynamics
PE	physical examination
PK	pharmacokinetic, pharmacokinetics
$ppFEV_1$	percent predicted forced expiratory volume in 1 second
PR	PR interval, segment
q12h	every 12 hours
qd	once daily
	the portion of an ECG comprising the Q, R, and S waves, together representing ventricular
QRS	depolarization
QT	QT interval
QTcF	QT interval corrected by Fridericia's formula
RR	interval from the onset of 1 QRS complex to the next
SAE	serious adverse event
SAP	statistical analysis plan
SD	standard deviation
SE	standard error

Abbreviation	Definition
SI	SI units (International System of Units)
SUSAR	suspected, unexpected, serious adverse reaction
SwC1	sweat chloride
TC	triple combination
TE	treatment-emergent
TEAE	treatment-emergent adverse event
TEZ	tezacaftor
ULN	upper limit of normal
US	United States

5 INTRODUCTION

5.1 Background

Cystic fibrosis (CF) is an autosomal recessive disease with serious, chronically debilitating morbidities and high premature mortality and, at present, has no cure. CF affects approximately 70,000 individuals worldwide.¹

CF is caused by a defect in the gene encoding the CFTR protein, an epithelial chloride (Cl⁻) ion channel that is responsible for aiding in the regulation of salt and water absorption and secretion in various tissues.² This function is defective in patients with CF due to a loss of cell surface expression and/or function of CFTR. Despite progress in the treatment of CF with antibiotics and mucolytics, the predicted median age of survival for a person with CF is approximately 40 years.^{3,4}

The therapeutic activity of CFTR correctors and potentiators has been established with products that were developed by Vertex and approved for the treatment of CF (Kalydeco® and Orkambi®). Tezacaftor (TEZ; VX-661) is a first-generation CFTR corrector that improves the processing and trafficking of the F508del-CFTR protein, resulting in an increase in the quantity of F508del-CFTR protein at the cell surface. Ivacaftor (IVA) increases the open-channel probability of the F508del-CFTR protein that has been delivered to the cell surface by TEZ, thereby enhancing total chloride transport. The combined effect of TEZ and IVA is increased quantity and function of F508del-CFTR at the cell surface.

VX-659 is a next-generation CFTR corrector. In vitro, the triple combination (TC) of VX-659, TEZ, and IVA (VX-659/TEZ/IVA) increased CFTR chloride transport in *F508del/F508del*-human bronchial epithelial (HBE) cells more than any of the dual combinations (VX-659/TEZ, VX-659/IVA, and TEZ/IVA) or individual components (VX-659, TEZ, and IVA) under most conditions studied.⁵

